# 13.2 Statistical Analysis

The primary analysis study population will be intent-to-treat in that all patients receiving the 1st injection of HCW9218 will be evaluable for toxicity and efficacy.

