# 5.3 Inability to Begin Study Treatment

If a patient is enrolled to the study and is later found not able to begin study treatment, for whatever reason, the patient will be taken off study and treated at the physician's discretion. The Study Coordinator or designee will update OnCore of the patient's non-treatment status. The patient will be replaced to fulfill enrollment requirements and will not be included in the outcome analysis.

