# 6.2.1 STAGE 1 STEP 1 - Fast-track design (1 patient per dose level)

Start at DL1, enroll 1 patient per DL separated by a minimum of 21 days (DLT period) until the:

- 1st pre-defined adverse event Any of the following treatment emergent Grade 2 events lasting >72 hours within 5 days of 1st dose of HCW9218: fatigue, flu-like symptoms or injection site reaction.
- And the patient completes the 21 day DLT period with no DLT- Activate
   Stage 1 Step 2 in Section 6.2.2.

OR

1st DLT event within 21 days after the 1st dose of HCW9218 - Activate
 Stage 2 in Section 6.2.3 - Stage 1 Step 2 is not used.

OR

• 9 patients are treated at the DL4 - This completes enrollment - Stage 1 Step 2 and Stage 2 are not used.

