### 6.3 Monitoring for Dose Limiting Toxicities and Excessive Toxicity

Toxicity and adverse events are classified and graded according to NCI's Common Terminology Criteria for Adverse Events V 5.0 (CTCAE) unless otherwise noted in Section 10.

Note during the fast-track dose escalation only (Stage 1, Step 1), patients also are monitored for the pre-defined treatment emergent events defined in Section 6.2.1.

**Dose Limiting Toxicity (DLT)** is defined as any of the following treatment emergent adverse events using the NCI Common Terminology Criteria for Adverse Events (CTCAE) Version 5.0 within the 21 days after the 1st dose of HCW9218:

DLT event	Exceptions:		
Any Grade 3 or Grade 4 febrile neutropenia Any Grade 3 thrombocytopenia with bleeding Any Grade 3 or higher non-hematologic adverse event	
 
Grade 4 lymphopenia hat resolves to Grade 1 or lower (or to Baseline or lower, if pre-existing Grade 2 or higher) within 7 days
 
Grade 4 leukopenia that resolves to Grade 1 or lower (or to Baseline or lower, if pre-existing Grade 2 or higher) within 7 days
 
Grade 3 nausea, vomiting and/or diarrhea that last < 72 hours
 
Grade 3 or higher electrolyte abnormality that lasts < 72 hours, is not clinically complicated, and resolves spontaneously or responds to conventional medical interventions
 
Isolated Grade 3 elevation of ALT and/or AST that resolves to Grade 1 or lower (or to Baseline or lower, if pre-existing Grade 2 or higher) within 7 days
 
Grade 3 amylase or lipase that is not associated with symptoms or clinical manifestations of pancreatitis
 
		
	
 
Grade 3 fatigue, not due to disease progression, that lasts < 1 week
 
		
Hy's Law case (i.e., alanine aminotransferase/ aspartate aminotransferase (ALT/AST) >3 x ULN in combination with total bilirubin level (TBL) > 2 x ULN in the absence of cholestatic injury (ALP < 2 x ULN (Ricart, 2017; FDA, 2009)) and no other cause identified) after excluding biliary tract obstruction and liver metastasis  Inability to receive Cycle 2 dosing due to treatment related toxicity	MORE - I WOR		

The Dose Limiting Toxicity (DLT) Observation Period is defined as 21 days after the first dose of HCW9218. The DLT period does not end until the patient is assessed on Cycle 2 Day 1 (+3 days) and the results of lab work drawn on Cycle 2 Day 1 (+3 days) confirms no new DLTs since the previous assessment.

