# 6.7 Follow-Up for Disease Response and Survival (Duration of Study Participation)

After the End of Treatment visit follow up continues for 12 months from the 1st dose of HCW9218 to fulfill the secondary endpoints of disease status at 3, 6 and 12 months and progression free survival / overall survival at 6 and 12 months.

If a patient discontinued treatment for a reason other than disease progression, disease status is documented per standard of care reassessments until progression, and then for survival only until the end of the 12 month follow-up period.

Follow-up assessments may be in person, by medical record review, or local medical doctor if patient is no longer seen at the treating institution. In person follow-up visits solely for this research study are not required and may be linked with a standard of care visit. Refer to Section 8 for allowable time related windows around each follow-up time points.

Follow-up may end early if any of the following apply:

- The patient is discharged to hospice
- The patient withdraws consent
- The patient is lost to follow-up (defined as 3 missed appointments/attempts to contact)

If a patient dies before the end of the study defined follow-up, record the date of death as the off-study date and reason off study as death and add the date of death. Refer to Section 10.3 regarding reporting of deaths while a patient is on study.

If a person ends follow-up before the 12 month study period (i.e. withdraws consent, lost to follow-up), public records will be searched for survival information for the endpoints of survival at 6 and 12 months.

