## 13 Statistical Considerations

## 13.1 Study Design, Objectives and Endpoints

The purpose of this Phase I open-label study will be to identify the maximum tolerated dose (MTD) in a combined study group of all solid tumor cancers (except pancreatic cancer) and provide preliminary estimates of the response for future studies.

The primary endpoint is to provide the MTD of HCW9218 in advanced solid tumor cancers. The primary analysis will be intent-to-treat from the point of 1st injection of HCW9218 both for toxicity and efficacy. Patients who discontinue therapy prior to injection #1 will be replaced. We expect that the number of patients coming off therapy prior to injection #1 will be minimal/none.

There are 5 potential dose levels defined for Phase I. The trial will be conducted with no intra-patient escalation. The starting dose will be 0.25 mg/kg HCW9218 with a safety dose of 0.1 mg/kg HCW9218. The subsequent planned cohorts will be 0.5 mg/kg HCW9218, 0.8 mg/kg HCW9218 and 1.2 mg/kg HCW9218 (Table 1). Given that little to no toxicity is expected, the MTD will be determined using an adaptation of the continual reassessment method (CRM) (O'Quigley, 1996) starting with 1 patient cohorts.

Table 1.

Phase I HCW9218 Dose Levels					
Dose Level	HCW9218 dose				
-1	0.1 mg/kg				
1 (start)	0.25 mg/kg				
2	0.5 mg/kg				
3	0.8 mg/kg				
4	1.2 mg/kg				

This Phase I study will be conducted in two consecutive stages (non-CRM and CRM). A minimum of 21 days must separate each cohort. All patients are assessed for Dose Limiting Toxicity (DLT) per Section 6.3 as defined in the schema below:

**Stage 1 Step 1** uses a fast-track design (1 patient per cohort) with a minimum of 21 days between each patient until one of the following occurs:

The 1st occurrence of a **pre-defined treatment emergent adverse event** within 21 days of the 1st HCW injection (Section 6.2.1) at which point the study moves to **Step 2** and the cohort size increases from 1 to 3 patients with 2 additional patients added to the current cohort. A minimum of 21 days must separate each 3 patient cohort

- Escalation in Step 2 continues until the 1st DLT event at which point Stage 2
   (CRM) is activated. If Cohort 4 is completed without a DLT, Stage 2 (CRM) is not used.
- The 1st occurrence of a DLT at which point the study moves directly to Stage 2
  (CRM) as detailed below and Step 2 is not used.

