- Cohort 4 is completed without a pre-defined AE or a DLT neither Step 2 nor Stage 2 is used if a total of 9 patients are enrolled in Cohort 4 to complete the study.

Stage 2 is initiated at the 1st DLT. The study design changes to an application of the continual reassessment method (CRM) with an informative skeleton based on constrained maximum likelihood estimation (lasonos & O'Quigley, 2012). Enrollment occurs in cohorts of three patients. Each new cohort of three patients are sequentially assigned to the most appropriate dose by the study statistician based on the updated toxicity probabilities once the 3rd patient in a cohort reaches Day 21 (DLT period). The goal will be to identify one of the 5 dose level strategies corresponding to the desired maximum toxicity rate of ≤25%. The MTD will be identified by the minimum of the following criteria: (1) the total Stage 2 sample size of 24 is exhausted or (2) 9 consecutive patients are enrolled at the same dose. The function 'crm' from the R package 'dfcrm' will calculate posterior means of toxicity probabilities. Dose escalation of more than one level is not permitted with this design.

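### The all-injected toxicity set lets a patient whose DLT window was never completed count as DLT-free in dose decisions

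*Combined protocol and SAP*

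**What the plan says.** All references are to the combined protocol and SAP.

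- **Analysis set.** Section 13.2: "all patients receiving the 1st injection of HCW9218 will be evaluable for toxicity and efficacy". Section 13.1 and the Synopsis describe the primary analysis as intent-to-treat from the first injection. In Section 13.1 this directly follows the statement that the MTD is the primary endpoint. Section 13.2 adds only that the design determines the MTD.
- **Replacement.** Section 13.1: "Patients who discontinue therapy prior to injection #1 will be replaced". Section 5.3, on enrolled patients who cannot begin treatment: "The patient will be replaced to fulfill enrollment requirements and will not be included in the outcome analysis". Nothing is said about replacement after injection 1.
- **DLT window.** Section 6.3 sets 21 days after the first dose, then adds: "The DLT period does not end until the patient is assessed on Cycle 2 Day 1 (+3 days", with laboratory results from that visit showing no new DLT.
- **Counting rules.** Section 6.2.1: "9 patients are treated at the DL4 - This completes enrollment"; Section 6.2.2 has the same count. Section 13.1 says that neither Step 2 nor Stage 2 is used "if a total of 9 patients are enrolled in Cohort 4 to complete the study". Section 13.1 also speaks of Cohort 4 as *completed* without a DLT, but does not define the word. In Stage 2 the next cohort is assigned once the third patient reaches Day 21.
- **Review.** Section 11.4 has each patient's DLT status documented at the end of the first 21 days. It gives no category for an incomplete window.

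**The concern.** The escalation rules, the nine-patient count and the CRM each need a yes or no on DLT for every patient counted. The stated set admits anyone injected once, yet Section 6.3 says the window of a patient never assessed at Cycle 2 Day 1 has not closed. The two sections give different answers for the same patient, and none says which prevails.

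Following the analysis set, the unobserved days are scored as DLT-free. That under-counts DLTs and leans the MTD upward. In Stage 1 Step 1, where a level holds one patient, a single unobserved patient could clear it. The Revision History entry of March 29, 2023 reports no DLTs through dose level 4, so the exposure now is mainly the count of nine at that level. Reaching nine with no DLT ends enrollment without the CRM.

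**Working it through.** **Inputs from the documents.** Target DLT rate at most 25% and maximum 24 patients (Section 13.3); nine patients at dose level 4 (Sections 6.2.1, 6.2.2, 13.1); 21-day window (Section 6.3).

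**Assumed, because the documents give no figure.** A share *d* of injected patients is lost before the window closes: 5%, 10% or 20%. Loss times are uniform over 21 days and independent of DLT. DLT timing is either uniform over the window or confined to Days 1–7.

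**The plan's own figures.** Table 2 patient numbers sum to 0+1+1+1+9 = 12 (expected scenario) and 3+6+9+5+1 = 24 (excessive scenario), matching the stated minimum and maximum. The table shows no allowance for incomplete windows. Its selection probabilities cannot be reproduced exactly, because the skeleton is left until Stage 2.

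**Who is affected.** Injected patients who become unobservable, without a DLT, before the Section 6.3 assessment. Not affected are patients who stop treatment but are still assessed then, patients who miss Cycle 2 because of treatment-related toxicity (itself a DLT) and fatal non-hematologic events in the window (Grade 3 or higher, so a DLT).

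**Rule as written.** A DLT is missed if loss comes first. With loss uniform over 21 days, that chance is *d* × (mean DLT time)/21:

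- uniform timing: *d* × 10.5/21 = *d*/2, so the recorded rate is p(1 − d/2)
- Days 1–7: *d* × 3.5/21 = *d*/6, so the recorded rate is p(1 − d/6)

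P(0 of 9) = (1 − recorded rate)^9. With full observation and p = 0.25 this is 0.75^9 = 7.5%.

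**With replacement.** The DLT rate among evaluable patients is r = rec/[rec + (1 − p)(1 − d)], where rec is the recorded rate above, and P(0 of 9) = (1 − r)^9.

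Results at a true rate of 25%:

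| DLT timing | d | Recorded rate as written | P(0 of 9) as written | Rate among evaluable | P(0 of 9) with replacement |
|---|---|---|---|---|---|
| Uniform | 5% | 24.4% | 8.1% | 25.5% | 7.1% |
| Uniform | 10% | 23.8% | 8.7% | 26.0% | 6.6% |
| Uniform | 20% | 22.5% | 10.1% | 27.3% | 5.7% |
| Days 1–7 | 5% | 24.8% | 7.7% | 25.8% | 6.8% |
| Days 1–7 | 10% | 24.6% | 7.9% | 26.7% | 6.1% |
| Days 1–7 | 20% | 24.2% | 8.3% | 28.7% | 4.8% |

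At a true rate of 40%, P(0 of 9) is 0.60^9 = 1.0% with full observation and at most 1.8% as written.

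**Upper bound on the effect.** If one or two of the nine gave no DLT information at all, P(0 recorded) at a true 25% would be 0.75^8 = 10.0% or 0.75^7 = 13.3%. With no DLTs, the one-sided 95% upper limit, 1 − 0.05^(1/n), is 28.3% for nine complete windows, 31.2% for eight and 34.8% for seven.

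**The case against.** *The plan never says such a patient counts as DLT-free.* Correct. A reader might infer a stated rule that lost patients are scored as non-DLTs and may not be replaced. The documents do not go that far: the scoring follows from the all-injected set, and the replacement text is silent after injection 1. The word *completed* in Section 13.1, and the completed 21-day period in the Step 2 trigger of Section 6.2.1, point the other way. But *completed* is undefined, and the trigger governs only the move to Step 2. The contradiction remains.

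*Section 13.2 may govern only the adverse-event and response summaries.* Possible, but Section 13.1 places the intent-to-treat sentence directly after the MTD endpoint.

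*Section 6.7 deals with withdrawal and loss.* It foresees loss ("The patient is lost to follow-up (defined as 3 missed appointments/attempts to contact") and gives a fallback for survival ("public records will be searched for survival information for the endpoints of survival at 6 and 12 months"), but it concerns follow-up after the End of Treatment visit. It supplies no rule for the DLT window, and no rule should be read into it.

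*Active monitoring could stop at an early End of Treatment visit.* A reader might infer this from Sections 6.6 and 10.2. It does not stand: the Section 10.2 table keeps DLT documentation open until the DLT assessment is done.

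*Early loss should be rare.* Patients have ECOG status 0–1, attend one center and have frequent Cycle 1 visits. The pre-defined events are looked for within 5 days, which suggests early toxicity. This is a fair case for the lower end of the range.

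*Replacement is no more accurate.* This stands. With DLTs in Days 1–7, its upward bias is roughly four times the present downward one; at d = 20% it is +3.7 against −0.8 points. With uniform timing the two are similar: +2.7 against −2.5. One might expect replacement to restore 7.5%; under this model it gives 4.8–7.1%.

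**Conclusion.** The concern holds in a limited form and should be fixed. The stated toxicity set lets an incomplete window count as DLT-free in dose decisions, in conflict with Section 6.3, and no section resolves the conflict.

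The effect is small and in the less safe direction. At a true 25% DLT rate, the chance of finishing nine patients at dose level 4 with no DLT moves from 7.5% to 7.7–10.1%. This rests on an assumed 5–20% loss, uniform in time and independent of DLT. The 10.0% and 13.3% figures are extremes, because a patient lost partway still contributes the days observed.

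A reader might infer a material distortion of CRM dose selection. No size can be claimed. Approximate simulations with three assumed skeletons and full observation chose a dose above the 25%-DLT dose in 20–29% of trials, against 34% + 1% = 35% in Table 2. They show the direction only, which is upward.

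**What to change.** 1. Keep the all-injected set for adverse-event tables and efficacy.
2. For escalation, the nine-patient counts and the CRM, define a DLT-evaluable set: the patient had a DLT, or was assessed through the end of the Section 6.3 DLT period.
3. Replace other injected patients for dose decisions, within the cap of 24. If the cap is reached, do not replace.
4. Report the MTD with the number of complete windows. If the cap prevented replacement, add a sensitivity analysis on all injected patients.
5. Add a category for a DLT window not completed to the Section 11.4 review.

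**Cost.** A few sentences in Sections 6.2, 11.4, 13.1 and 13.2, an occasional extra patient and about 3 weeks when one is needed. Mean extra patients for *w* complete windows are w × d/(1 − d), at d = 5%, 10% and 20%:

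- nine at dose level 4: 0.5, 1.0, 2.3
- 12 windows (three single-patient levels plus nine): 0.6, 1.3, 3.0
- 18 windows (three levels of three plus nine): 0.9, 2.0, 4.5

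The chance of needing more than 24 patients (negative binomial) is under 0.1% on the 12-window path. On the 18-window path it is under 0.1%, 0.8% and 19%. Paths that already use 24, as in Table 2's excessive scenario, leave no room for replacement, hence item 3. The evaluable rate leans cautious (25.5–28.7% at a true 25%), so the gain is safety and an honest denominator rather than an unbiased rate.

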# **Primary Endpoint**

The MTD will be determined by design.

# **Secondary Endpoints**

If there are sufficient numbers, the secondary endpoints of overall survival and progression-free survival by 6 months and 1 year will be estimated with Kaplan-Meier curves. The primary efficacy endpoint of response rate will be estimated by a simple proportion with 95% confidence limits if sufficient numbers exist. Safety will be estimated by the proportion of adverse events based on CTCAE v5. Further descriptive statistics and plots such as boxplots, spaghetti plots and swimmer plots will be used to assess kinetics and other markers of efficacy such as immune based monitoring and toxicity.

## 13.3 Sample Size

A maximum of 24 patients will be enrolled with a target DLT rate of ≤25%. Based on the simulations from Table 2, this should be sufficient and safe to define the MTD. Although complete skeleton estimates will not be determined until Stage 2, Table 2 is calculated based on hypothesized values.

Table 2. Operating characteristics for Adaptive-CRM

-	_		•				
	Expected DLT,	Expected	SAE 	Excessive DLT, Excessive SAE			
HCW9218 Dose	True	Prob. of	$N^4$	True	Probability	N	
Levels	Probability	dose 		Probability	of dose		
0.1 mg/kg (-1)	0.5%, 0.5%	0%	0	5%, 18%	3%	3	
0.25 mg/kg (1, start)	0.75%, 1.5%	0%	1	10%, 29%	18%	6	
0.5 mg/kg (2)	1.5%, 3%	0%	1	25%, 50%	44%	9	
0.8 mg/kg (3)	3%, 5%	0%	1	40%, 66%	34%	5	
1.2 mg/kg (4)	7%, 7.5%	100%	9	55%, 77%	1%	1	

- 1. SAE's without a DLT trigger step 2 in stage 1, DLT's regardless of SAE's trigger stage 2
- 2. Expected/Excessive values are the hypothesized true values under the simulation
- 3. Probability of dose chosen as the MTD using the Adaptive-CRM design
- 4. The hypothesized number of patients enrolled at each dose during the trial under the assumed hypothesized "true" probabilities

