#### **Enrollment Goal:**

A minimum of 12 patients or a maximum of 24 if DLT is encountered.

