# 3 Study Plan

This is a single center Phase I dose finding study of HCW9218 for the treatment of select advanced solid tumor cancers, including, but not limited to breast, ovarian, prostate and colorectal. Pancreatic cancer is excluded due to a competing HCW9218 protocol. Primary brain tumors are not eligible.

HCW9218 is a novel bi-functional fusion protein complex administered by subcutaneous (SC) injection. It is comprised of a soluble fusion of two human TGF $\beta$ RII domains, human tissue factor, and human IL-15, and a second soluble fusion of two human TGF $\beta$ RII domains and a sushi domain of human IL-15R $\alpha$ . HCW9218 activates IL-15R signaling on effector immune cells and the dimeric TGF $\beta$ RII functions as a "trap" for all three human TGF- $\beta$  isoforms.

HCW9218 is administered by subcutaneous injection in the outpatient setting once every 3 weeks for a minimum of two cycles unless medically contraindicated or the participant wishes to discontinue treatment as detailed in Section 6.6. Treatment may continue until disease progression, unacceptable toxicity, patient refusal, or treatment is felt to be no longer of benefit. Patients are followed for 12 months from the 1st dose of HCW9218 to determine progression free survival (PFS) and overall survival (OS).

Dose Level (DL) Cohort	HCW9218 Dose (mg/kg)	Enrollment Plan		
-1	0.1	Administer HCW9218 as monotherapy at assigned dose by		
1 (start)	0.25	SC injection once every 3 weeks.		
2	0.5	All patients are assessed for AEs and dose limiting toxicities (DLT). A minimum of 21 days must separate each dose		
3	0.8	cohort. Within a 3 patient dose cohort, a minimum of 14 days must separate the 1st and 2nd patient.		
4	1.2			

The maximum sample size will be 24 patients.

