# 6.2.3 STAGE 2 Continual Reassessment Method (CRM)

The study design changes to an application of the continual reassessment method (CRM). Enrollment occurs in cohorts of three with a minimum of 14 days between the 1st and 2nd patient. Each new cohort of three patients are sequentially assigned to the most appropriate dose by the study statistician based on the updated toxicity probabilities once the 3rd patient in a cohort reaches Day 21 (DLT period). The goal will be to identify one of the 4 dose level strategies corresponding to the desired maximum toxicity rate of ≤25%. The MTD will be identified by the minimum of the following criteria: (1) the total Stage 2 sample size of 24 is exhausted or (2) 9 consecutive patients are enrolled at the same dose.

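### Stage 2 may run to 24 patients on its own, but the whole trial is capped at 24 and Stage 1 has already used at least one place

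*Combined protocol and SAP*

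**What the plan says.** Three places limit the whole trial to 24 patients:

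- Section 13.3: "A maximum of 24 patients will be enrolled with a target DLT rate of ≤25" per cent.
- Section 3: "The maximum sample size will be 24 patients".
- Synopsis, Enrollment Goal: "A minimum of 12 patients or a maximum of 24 if DLT is encountered".

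The rule that ends the CRM is written differently. Section 6.2.3 identifies the MTD at the earlier of two events: "the total Stage 2 sample size of 24 is exhausted or (2) 9 consecutive patients are enrolled at the same dose". The Synopsis and Section 13.1 use the same wording.

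Two further statements in Section 13.1 matter here. On timing: "Stage 2 is initiated at the 1st DLT". On cohort size: "Enrollment occurs in cohorts of three patients". Before that point, Stage 1 enrols one patient per dose level (Step 1) or three (Step 2). With no DLT it ends at dose level 4 (DL4): "9 patients are treated at the DL4 - This completes enrollment" (Section 6.2.1).

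**The concern.** The figure 24 is attached to two different counts: all patients in the trial, and Stage 2 patients only. They cannot be the same count, because the DLT that opens Stage 2 belongs to a patient treated in Stage 1.

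Section 13.2 gives no analysis of the primary endpoint beyond saying that the design determines the MTD, so the rule that ends Stage 2 is in effect the primary analysis. A statistician who counts from the first Stage 2 patient may take enrolment past the stated maximum. One who applies the trial maximum has fewer Stage 2 patients than the criterion names, and must also decide what to do when the places left do not divide into threes. Section 13.3 calls 24 sufficient and safe on the strength of Table 2, without saying which count was simulated.

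**Working it through.** **1. The plan's own figures.** The 24 is a design cap, not the result of a power formula, so the check is a count.

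- Minimum of 12: one patient at each of DL1 to DL3 and nine at DL4, 1 + 1 + 1 + 9 = 12. The Enrollment Goal therefore counts Stage 1 patients.
- Table 2, N column, Expected: 0 + 1 + 1 + 1 + 9 = 12.
- Table 2, N column, Excessive: 3 + 6 + 9 + 5 + 1 = 24. Footnote 4 describes these as numbers for the trial, not for Stage 2.

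**2. Literal reading.** Total limit = N1 + 24, where N1 is the number treated in Stage 1.

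- Smallest: DLT in the first DL1 patient, 1 + 24 = 25.
- Largest without Step 2: DLT in the ninth DL4 patient, (1 + 1 + 1 + 9) + 24 = 36.
- Largest with Step 2 from DL1: (3 + 3 + 3 + 9) + 24 = 42.

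**3. Overall cap.** Stage 2 places = 24 − N1. The most is 24 − 1 = 23 and the fewest is 24 − 18 = 6. Criterion (1) as worded is never reached.

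**4. Typical size of N1.** Stage 1 was enumerated exactly from Table 2's rates for DL1 to DL4:

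- Expected: DLT 0.75, 1.5, 3 and 7%; SAE 1.5, 3, 5 and 7.5%.
- Excessive: DLT 10, 25, 40 and 55%; SAE 29, 50, 66 and 77%.

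Following footnote 1, an SAE without a DLT triggers Step 2 and a DLT triggers Stage 2. Assumptions: patients independent, DLT and SAE independent within a patient, DL4 filled to nine, Stage 1 stopped at the DLT patient.

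| Scenario | P(Stage 2) | Mean N1, if Stage 2 opens | 24 − mean N1 | Places left not a multiple of 3 |
|---|---|---|---|---|
| Expected | 0.51 | 7.2 | 16.8 | 67% |
| Excessive | >0.999 | 4.1 | 19.9 | 71% |

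Other assumptions about how DLT and SAE occur together, and the alternative DL4 wording, give 16.8–17.3 and 19.8–20.1 places, with 66–71% and 70–72% not divisible by three. If open cohorts are completed before Stage 2 starts, the places left are about 16–17.5 and 19–20. The share not divisible by three then depends on how DL4 is filled: 12–29% (Expected) and 59–65% (Excessive). The simplest case shows the gap: N1 = 1 leaves 23 = 7 × 3 + 2, a last cohort of two, for which there is no rule.

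**5. How often the literal limit would be passed (illustrative).** The documents give no skeleton or prior, so these inputs are assumed: power model, normal prior with variance 1.34, target 25%, cohorts of three, the nine-consecutive rule and the 80% toxicity stop. Across 64 settings (16 skeletons, two Stage 1 conventions, Stage 1 patients counted or not towards the nine; 4,000 trials each), the total passed 24 in:

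- Expected: 0.1–3% of trials.
- Excessive: 6–68% of trials, median 24%. Where it passed 24, the total averaged about 27–29.

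A separate simulation with two other assumed skeletons gave 1–2% and 20–28%.

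**6. Whether Table 2 settles the reading.** It does not. In that separate simulation the mean total under Excessive was 18.5–19.3 (overall cap) or 19.2–20.5 (literal) with the nine-consecutive rule, and 24.0 or 28.2 without it. A column sum of 24 does not identify the cap that was used.

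**The case against.** The best defence is that the documents already answer the question. Two sections state an unqualified trial maximum of 24, and the Enrollment Goal applies 24 to exactly the case in which a DLT occurs and Stage 2 is used. On that view the Stage 2 wording is loose phrasing for the trial total. A stopping limit is not permission to exceed a maximum, and this is a drafting slip with no effect on the design.

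Much of this stands. 24 overall is the more natural reading, and the conflict is dormant whenever another rule ends Stage 2 first. The overrun percentages depend on assumed skeletons and vanish under the overall cap, so they should carry little weight. A CRM update can also use a last cohort of one or two patients, so the short-cohort point is a request for clarity.

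The defence does not remove the contradiction. The Stage 2 wording appears three times, unchanged, in the rule that staff will apply, and nothing says that Stage 1 patients count towards it.

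It can also be said that the simulated averages describe a trial from its start, whereas the March 2023 revision entry reports no DLTs from DL1 to DL4. That is fair, but it widens the gap. If at least one patient had been treated at each of the four levels, N1 is at least 4. The literal limit is then at least 4 + 24 = 28, and an overall cap leaves at most 24 − 4 = 20 places.

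**Conclusion.** The point holds. The trial maximum and criterion (1) cannot both be correct as written: the literal limit is 25 to 42 patients against a stated maximum of 24, and the overall cap leaves 6 to 23 Stage 2 places against the 24 named. This follows from counting alone. It needs only the fact that the first DLT occurs in a Stage 1 patient.

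The practical effect is confined to trials that neither the nine-consecutive rule nor the toxicity stop ends first. That is uncommon at Table 2's Expected rates. At the Excessive rates it could be frequent, but how frequent cannot be settled without the skeleton. The correction is small, but it is needed because this rule determines the primary endpoint.

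**What to change.** - In the Synopsis, Section 6.2.3 and Section 13.1, reword criterion (1) so that it is met when 24 patients in total, Stages 1 and 2 combined, have been enrolled.
- Add one sentence on a last cohort with fewer than three places left: whether it is enrolled short or not opened.
- If 24 was meant for Stage 2 alone, leave criterion (1) and restate the trial maximum in the Synopsis, Section 3 and Section 13.3.
- State which cap Table 2 was simulated under, and rerun it if it was the other one.

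The cost is one phrase in three places and one added sentence. Keeping the overall cap adds no patients, and new simulation is needed only if Table 2 used the other cap.

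A separate, minor point can be settled in the same edit. Section 6.2.2 and the Synopsis close enrolment without Stage 2 once nine patients have been treated at DL4, whereas Section 13.1 makes this conditional on no DLT. The two should be reconciled for a DLT that emerges after the ninth patient is treated.

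### The 24-patient limit is stated two ways, as a whole-trial maximum and as a Stage 2 cap on top of Stage 1, and Table 2 does not clearly describe the 24-patient trial it is used to justify

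*Combined protocol and SAP*

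**What the plan says.** **Whole-trial limit.** Section 13.3: "A maximum of 24 patients will be enrolled with a target DLT rate of ≤25" (percent). Section 3: "The maximum sample size will be 24 patients". Enrollment Goal in the synopsis: "A minimum of 12 patients or a maximum of 24 if DLT is encountered".

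**Stage 2 limit.** Section 13.1 names the MTD at whichever comes first: "1) the total Stage 2 sample size of 24 is exhausted or (2) 9 consecutive patients are enrolled at the same dose". The synopsis (Stage 2) and Section 6.2.3 carry the same rule.

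**Cohorts.** Stage 1 starts with one patient per dose. After a pre-defined adverse event, "the cohort size increases from 1 to 3 patients with 2 additional patients added to the current cohort". Stage 2 opens at the first DLT, and then "Enrollment occurs in cohorts of three patients". Section 13.4 adds a stop when the posterior probability that the lowest dose exceeds a 25% DLT rate is above 80%.

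**Table 2 (13.3).** In the Excessive scenario the DLT rates are 5/10/25/40/55% from level -1 to level 4, N is 3/6/9/5/1, and the selection probabilities are 3/18/44/34/1%. In the Expected scenario N is 0/1/1/1/9. Footnote 4 defines N as "The hypothesized number of patients enrolled at each dose during the trial under the assumed hypothesized" true probabilities. The section says skeleton estimates are not determined until Stage 2. The table does not state the cap, the stopping rules or the number of simulated trials behind it.

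**The concern.** The Excessive N column adds to 24, exactly the stated trial maximum. Yet the design can stop early, once "2) 9 consecutive patients are enrolled at the same dose", and it adds whole cohorts of three to a Stage 1 of varying size. A trial limited to 24 with those rules should average clearly fewer than 24. If the simulation instead allowed 24 patients in Stage 2 alone, it describes a trial that can exceed the stated maximum.

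Table 2 is the only quantitative support for the sample size and for the stated chances of choosing each dose. A reader of 13.3 cannot tell which trial those figures belong to, or how many patients may be enrolled.

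**Working it through.** **1. The plan's own figures.** Excessive N: 3 + 6 + 9 + 5 + 1 = 24. Selection: 3 + 18 + 44 + 34 + 1 = 100%. Expected N: 0 + 1 + 1 + 1 + 9 = 12. If N is a rounded mean, the unrounded Excessive total lies between 2.5 + 5.5 + 8.5 + 4.5 + 0.5 = 21.5 and 3.5 + 6.5 + 9.5 + 5.5 + 1.5 = 26.5.

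**2. Stage 2 cap, by arithmetic.** Stage 2 opens at the first DLT, so Stage 1 holds n1 ≥ 1 patients. The largest Stage 1 is 3 + 3 + 3 + 9 = 18. A trial that exhausts a Stage 2 cap of 24 enrols n1 + 24, which is at least 25 and at most 42. Every such trial breaks the maximum of 24.

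**3. Whole-trial cap, bound without a skeleton.** Ignore the nine-consecutive stop and fill up with whole cohorts of three. Total N is then n1 + 3 × floor((24 − n1)/3): n1 = 1 gives 22, n1 = 2 gives 23, n1 = 3 gives 24. Weighting by the distribution of n1 at Table 2's Excessive rates (adverse event and DLT taken as independent) gives a mean of 22.9 to 23.0, depending on whether a Stage 1 cohort is completed after its first DLT. Only 29 to 38% of trials can land on exactly 24.

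**4. Simulation of the Excessive scenario.** The skeleton and prior are assumptions, because the documents give neither. The main set used a one-parameter power model, prior variance 1.34, target 25%, no upward skipping, the 80% stop, eight skeletons and 2,000 trials per setting.

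| Cap and rules | Mean total N |
|---|---|
| 24 whole trial, nine stop, whole cohorts | 17.0 to 21.5 |
| As above, last cohort may pass 24 | 17.2 to 22.5 |
| 24 whole trial, no nine stop, whole cohorts | 22.7 to 23.0 |
| 24 whole trial, no nine stop, last cohort cut at 24 | 23.7 to 24.0 |
| 24 in Stage 2 plus Stage 1, nine stop | 17.5 to 24.9 |

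- In the first row the nine stop ended about 31 to 89% of trials. The largest mean (skeleton 0.141/0.192/0.250/0.312/0.375, highest dose at or below 25%) had cells 3.0/5.9/7.1/4.0/1.4. The 7.1 at level 2 would need to be at least 8.5 to print as 9.
- A wider set of 648 settings under the whole-trial cap with the nine stop (27 skeletons, three prior variances, two dose-choice rules, Stage 1 counted or not toward nine, whole or short last cohort; 500 trials each) gave means of 14.3 to 23.0, median about 20. About a quarter reached 21.5. None reproduced the five cells.
- In the last row, the same closely spaced skeleton with the closest-to-25% rule gave a mean of 24.6 and cells 2.4/6.1/8.8/5.3/2.1. That is near the table, but level 3 was selected in about 24% of trials against 34% printed. Single trials under this cap reached roughly 34 to 39 patients.

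**5. Selection rates under the whole-trial cap.** Across five assumed skeletons with the nine stop, the 25%-DLT dose was chosen in 39 to 61% of trials (Table 2: 44%) and the 55%-DLT dose in 1.4 to 7.1% (Table 2: 1%).

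**6. Is N a mean? The Expected column.** On the shortest path (1 + 1 + 1 + 9 = 12) the chance of no DLT is 0.9925 × 0.985 × 0.97 × 0.93⁹ = 49%. Simulated mean totals were 14.7 to 16.1 across two sets of skeletons, with about 11 at level 4. Rounding of the printed cells allows only 10.0 to 14.5. Per-dose medians were 0/1/1/1/9 in all 12 runs in which they were computed, exactly as printed.

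**The case against.** A reader might infer that Table 2 is impossible, or that it simulates a different trial from the one in 13.1. The documents do not support that, for four reasons.

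- Section 13.1 itself caps Stage 2, not the trial. With that cap, cohorts of three and the nine stop all in force, a mean near 24 is attainable.
- Footnote 4 never calls N a mean, and the Expected column fits medians better. Medians need not add to a trial size, so their sum cannot be held against a cap. For the Excessive column, two closely spaced skeletons under the Stage 2 cap gave medians of 3/6/9/5/0, against 3/6/9/5/1 printed.
- Even as means, rounding allows a total as low as 21.5, and the bound of 23.0 lies inside that range.
- The skeletons tried are fixed and assumed, whereas 13.1 calls for an informative skeleton from constrained maximum likelihood. Failure to reproduce the cells is evidence, not proof.

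All four stand. One could also read the Stage 2 wording as a running total that includes Stage 1. The three places do not say so, and that is the ambiguity to remove. None of this settles the conflict over the cap. The reading that best fits Table 2's total also lets trials exceed the maximum that 13.3 states.

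**Conclusion.** The point holds as an unreconciled cap and an under-specified table. If 24 applies to Stage 2, the stated trial maximum of 24 is not kept: any trial reaching that cap has at least 25 patients, and simulated single trials reached roughly 34 to 39. If 24 applies to the whole trial, simulated mean total N in the Excessive scenario is about 17 to 22 over most assumed skeletons (14.3 to 23.0 over the widest set), and no setting with the nine stop gave the printed cells. Either way, Table 2 does not clearly support the 13.3 conclusion about a 24-patient trial.

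The arithmetic in steps 1 and 2 needs no model. The bound in step 3 assumes only Table 2's rates, whole cohorts, and independence of adverse event and DLT. The simulated ranges, including the selection rates, depend on assumed skeletons and priors, so they show the possible size of the discrepancy and do not replace the printed figures.

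**What to change.** 1. Decide whether 24 limits the whole trial or Stage 2 alone, and state it identically in the synopsis (Stage 2 and Enrollment Goal) and in Sections 3, 6.2.3, 13.1 and 13.3. If the Stage 2 cap is kept, restate the maximum enrolment to include Stage 1. If the whole-trial cap is kept, say what happens when fewer than three places remain.
2. Re-run Table 2 under that cap with cohorts of three, the nine-consecutive stop and the 80% stop in force.
3. State the skeleton and prior, the number of simulated trials, and whether N is a mean or a median.
4. Report mean and maximum total N and the share of trials ended by each rule, and restate the 13.3 conclusion on those figures.

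The cost is a few hours of simulation, a replaced table and matching edits in the sections listed. Some stated figures may become less favourable. A Stage 2 cap would also raise the stated maximum enrolment above 24.
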